## 4.2. Final Analysis

The final analysis will use the same populations as above, plus additional populations as defined below.

Population	Definition / Criteria	Analyses Evaluated
PK	
 
All participants in the mITT population who had at least 1 non-missing PK assessment (Non-quantifiable [NQ] values will be considered as non-missing values) obtained and analysed whilst on treatment with danirixin.
 
	
 
PK
 

PK2	
 
All participants in the PK population who had at least 1 non-missing PK assessment (NQ values will be considered as non-missing values) obtained and analysed whilst on treatment with danirixin from a dry blood spot sample and corresponding wet whole blood sample.
 
	
 
PK Dry Blood Spot vs Wet Whole Blood
 

Refer to [Appendix 11](#): List of Data Displays which details the population used for each display.

In the event one or more investigators are withdrawn from the study due to concerns over protocol deviation then a further population will be defined which will consist of all participants in the PP population excluding participants from those investigative sites. This population will be used to perform additional sensitivity analysis for the primary efficacy endpoint only and will only be defined if the combined enrolment at these sites exceeds  $\geq 2\%$  of the overall PP study enrolment. No other analyses will be repeated.

## 4.3. Protocol Deviations

Protocol Deviations (PDs) will be tracked by the study team throughout the conduct of the study in accordance with the Protocol Deviation Management Plan (6JUL2018, V2.0):

- Data will be reviewed prior to SDL to ensure all important deviations are captured and categorised on the protocol deviations dataset.
- Participants who received an incorrect treatment container will be captured as an important protocol deviation. Whether or not the incorrect container contained incorrect treatment will be identified following DBF in the analysis dataset and the PD will be flagged accordingly.
- This dataset will be the basis for the summaries and listings of protocol deviations.
- Important protocol deviations (including deviations related to study inclusion/exclusion criteria, conduct of the trial, participant management or participant assessment) will be summarised and listed.
- A separate summary and listing of all inclusion/exclusion criteria deviations will also be provided. This summary will be based on data as recorded on the inclusion/exclusion page of the electronic case report form (eCRF).

## 5. CONSIDERATIONS FOR DATA ANALYSES AND DATA HANDLING CONVENTIONS

### 5.1. Study Treatment & Sub-group Display Descriptors

Treatment Group Descriptions			
RandAll NG		Data Displays for Reporting	
Code	Description	Description	Order in TLF
D5	Danirixin 5mg	DNX 5mg	2
D10	Danirixin 10mg	DNX 10mg	3
D25	Danirixin 25mg	DNX 25mg	4
D35	Danirixin 35mg	DNX 35mg	5
D50	Danirixin 50mg	DNX 50mg	6
PO	Placebo oval	Placebo	1
PR	Placebo round	Placebo	1

Treatment comparisons will be displayed as in the danirixin dose column with the descriptor: Column vs Placebo.

### 5.2. Baseline Definitions

Any assessments made after the start of study treatment will not be included in the derivation of baseline. Assessments made on the same day as the start of treatment are assumed to be taken prior to first dose.

If baseline data are missing, no derivation will be performed and baseline will be set to missing.

Parameter	Baseline Used in Data Display
E-RS: COPD total and subscale scores	Mean score during a stable period between (Latest of (7 days before Study treatment start date (Day 1) and day of Visit 1 (Screening)) and day before Day 1 of study treatment. Data must be present on at least 4 days
EXACT (for determining EXACT events)	Defined according to the EXACT User Manual v8.0 ( Evidera, 2016a )
SGRQ total and domain scores	Day 1
CAT score	Day 1
Rescue use (diary card and sensor data, mean number of puffs/occasions per day and percentage of rescue-free days)	Mean score during a stable period between (Latest of (7 days before Study treatment start date (Day 1) and day of Visit 1 (Screening)) and day before Day 1 of study treatment. Data must be present on at least 4 days.
PROactive score	A PROactive Total Score and two domain scores (amount and difficulty) will be derived using data from the C-PPAC questionnaire on Day 1 and physical activity

Parameter	Baseline Used in Data Display
	monitor worn between Visit 2 and Visit 3 (7 days). The activity monitor must have been worn for at least 3 days with $\geq 8$ hours wearing (the 3 days do not need to be consecutive). Further details of the derivation are described in Section 14.6.3 and in the IMI PROactive user manual (14JUN16).
Blood pressure (BP)	Latest pre-dose assessment with a non-missing value for both systolic and diastolic BP, including those from unscheduled visits
Pulse rate, laboratory data, ECG	Latest pre-dose assessment with a non-missing value for the individual assessment, including those from unscheduled visits
Post-bronchodilator (BD) FEV1, post-BD FVC	Day 1

### 5.3. Multicentre Studies

In this multicentre global study, enrolment will be summarized by country and investigative site. Country will be included as a fixed effect in statistical models and treatment by country interaction investigated as described in Section 7 and Section 8. Results will be presented for all countries combined except as specified in Section 7.

### 5.4. Examination of Covariates, Other Strata and Subgroups

#### 5.4.1. Covariates and Other Strata

The covariates and other strata listed below will be used in statistical models and treatment by covariate/stratum investigated as defined in Section 7, Section 14.6.2 and Section 14.6.3.

Category	Details
Strata	Smoking status
Covariates	Treatment, visit/Month, baseline, smoking status at screening, country, gender, exacerbation history ( $\leq 1$ , $\geq 2$ moderate/severe), post-bronchodilator % predicted FEV1, CMH status at baseline, season of data collection.

## 5.4.2. Examination of Subgroups

The subgroups listed below will be used in statistical analyses as described in Section 7.

Subgroup	Categories
Season	Spring, Summer, Fall, Winter (see Section 14.6.3)
Country	Australia, Canada, Germany, Korea, Netherlands, Poland, Romania, Spain, US
Exacerbation history	History of $\geq 2$ moderate/severe exacerbations vs $< 2$ moderate/severe exacerbation
COPD medication at Baseline	ICS+LABA+LAMA vs. ICS+LABA vs. LABA+LAMA vs. Other COPD medication
ERS10	Baseline E-RS: COPD Total Score $< 10$ , $\geq 10$
CAT10	Baseline CAT Score $< 10$ , $\geq 10$
Smoking status at Screening	Current, Former
% predicted FEV1 at Screening	$< 50\%$ , $\geq 50\%$
CMH status at baseline	CMH+, CMH- (see Section 14.6.2)

## 5.5. Multiple Comparisons and Multiplicity

No multiplicity adjustment will be made for this study, as the primary objective of the study is to model the danirixin dose response and use it to select Phase III dose(s).

## 5.6. Other Considerations for Data Analyses and Data Handling Conventions

Other considerations for data analyses and data handling conventions are outlined in the appendices:

Section	Component
14.3	Appendix 3: Assessment Windows
14.4	Appendix 4: Study Phases
14.5	Appendix 5: Data Display Standards & Handling Conventions
14.6	Appendix 6: Derived and Transformed Data
14.7	Appendix 7: Reporting Standards for Missing Data
14.8	Appendix 8: Values of Potential Clinical Importance

## **6. STUDY POPULATION ANALYSES**

### **6.1. Overview of Planned Study Population Analyses**

Study population displays including analyses of participant disposition, protocol deviations, demographic and baseline characteristics, prior and concomitant medications, and exposure and treatment compliance will be based on GSK Core Data Standards. Results will be presented for each treatment and overall.

Details of the planned displays including the population to be used for each display and which displays are produced for the strategic interim are presented in [Appendix 11](#). Additional details are provided below.

#### **6.1.1. Demographic and Baseline Characteristics**

The summary of exacerbation history at Screening will include the number and percentage of participants reporting mild, moderate, severe and moderate/severe exacerbations (0, 1, >=2; see Section [14.6.2](#)) in the 12 months prior to screening.

#### **6.1.2. Prior and Concomitant Medications**

Non-COPD medication tables will report by Anatomical Therapeutic Chemical (ATC) level 1 classification and ingredient. Multi-ingredient non-COPD medications will be presented according to their combination ATC classification rather than the classifications of the ingredients.

COPD medication tables will report by respiratory medication class (RMC) and ingredient (See Section [14.6.2](#)). The number and percentage of participants taking each medication in the RMC categories (defined in Section [14.6.2](#)) will be presented.

The number and percentage of subjects taking each medication in the RMC categories ICS, LABA, LAMA, PDE4 inhibitors, Xanthines, Anti-IgE, Anti-IL5 and combinations of these RMCs on the day of the Screening visit, at Baseline (Day 1) and at Month 6 will be presented.

#### **6.1.3. Exposure and Treatment Compliance**

Calculation of treatment compliance will be based on the number of tablets dispensed and returned as described in Section [14.6.2](#). Calculation of diary compliance will be based on the number of days with non-missing E-RS: COPD total score as described in Section [14.6.2](#). Percentage treatment and diary compliance will be summarized categorically and with descriptive statistics.

## 7. EFFICACY ANALYSES

Details of the planned displays including the population to be used for each display and which displays are produced for the strategic interim are presented in [Appendix 11](#). Additional details are provided below.

For this study, no data were scheduled to be collected after discontinuation of study treatment, therefore accounting for non-recorded missing data following study withdrawal is addressed by the strategy for the intercurrent event of treatment discontinuation.

### 7.1. Primary Efficacy Analyses

#### 7.1.1. Month 6 E-RS: COPD Total Score Dose-Response Analysis

The estimand is the effect of actual treatment in the population of participants who did not experience a protocol deviation considered to impact efficacy and completed six months of treatment.

A Bayesian dose response model will be applied to the change from baseline to Month 6 and used to estimate the treatment difference between placebo and each dose.

The dose-response model will be fitted using Bayesian techniques with non-informative priors for E0 and Emax and a functional uniform prior (FUP) for ED50 and the slope parameter, m ([Bornkamp, 2014](#)). The rationale for this choice of inference is that the FUP shrinks the dose-response towards a flat line throughout the dose range, therefore providing more conservative estimates of the dose-response relationship compared to maximum likelihood.

For the strategic interim, the posterior predictive probability of success (PPS) at the end of the study will be calculated for each dose using the formula suggested by Spiegelhalter et al. ([Spiegelhalter, 2004](#)) as follows:

$$PPS = \Phi \left[ \frac{\sqrt{(m+n)} \frac{(-my_m)}{\sigma_{trt\ diff}} + \sqrt{\frac{m}{n}} z_{0.9}}{\sqrt{mn}} \right]$$

Where m is the average number of participants with Month 6 data in the placebo and comparative dose arm, n is the average number of participants yet to be observed (assuming 90% of participants, rounded to the nearest integer, in each treatment group will provide month 6 data at end of study. If the actual number of participants at month 6 exceeds this, the actual number will be used),  $y_m$  is the posterior mean difference from the fitted model, and  $\sigma_{trt\ diff}$  is the standard deviation (SD) of the posterior mean difference.

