5.2. Number of Participants

Approximately 700 participants will be screened to achieve approximately 600 randomized participants. It is anticipated that approximately 540 participants will complete 24 weeks of treatment and key study assessment (the dropout rate is estimated to be approximately 10% based on previous experience with studies enrolling similar participants).

For the analysis of study assessments, several analysis populations will be defined. Details of the evaluable participants for each planned analysis population are included in Section 10.4.

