10.3. Randomization

Participants will be randomized equally (1:1:1:1:1:1) to the six treatment arms of placebo, 5 mg, 10 mg, 25 mg, 35 mg and 50 mg danirixin. Randomization will be stratified by smoking status (current vs. former).

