##### **3.1.3. Strategic Analysis**

When approximately 450 participants had completed 6 months of treatment, a further interim analysis was performed for strategic planning purposes, as described in this RAP. This analysis was planned to be used to aid in the planning of future studies and for a better understanding of benefit/risk profile of danirixin. No changes were made to the study based on the results of this strategic interim analysis.

The analyses were performed after the completion of the following sequential steps:

1. The date of the planned Visit 10 for the 450th completed participant (01AUG2018) had been met.
2. All required database cleaning activities had been completed by Data Management (DM) on data collected up until 01AUG18. Data collected between 02AUG2018 and 5SEP2018 (DBR) for ongoing subjects was not cleaned.
3. Unblinded randomization schedules were released by Randomization coordinator.

Data was reported in System Independent (SI) format. Outputs featuring unblinded treatment assignments were created for this strategic interim analysis, reviewed by the study team and shared with selective GSK personnel (to be included in the SRDP).

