**7.1.1.2. Summary Measure**

For the strategic interim, the summary measure is the posterior predictive probability of success for each danirixin dose, where success is the probability that a true difference from placebo is less than 0 is >95% at Month 6.

For the final analysis, the summary measure is the posterior probability that a true difference from placebo is less than 0 at Month 6 for each danirixin dose.

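### The strategic-interim probability-of-success formula does not match its own >95% criterion and counts the interim sample size twice, so trivial effects score as near-certain successes

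*SAP*

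**What the plan says.** SAP 7.1.1.2 makes PPS for each danirixin dose the summary measure at the strategic interim, "where success is the probability that a true difference from placebo is less than 0 is >95% at Month 6". The results presentation in SAP 7.1.1.5.1 repeats the 95% threshold.

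SAP 7.1.1 prints the calculation, as extracted, as

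`PPS = Φ{ [ √(m+n)·(−m·y_m)/σ_trt diff + √(m/n)·z_0.9 ] / √(mn) }`

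The inputs are defined in prose:

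- "m is the average number of participants with Month 6 data in the placebo and comparative dose arm".
- n is the average number still to be observed, "assuming 90% of participants, rounded to the nearest integer, in each treatment group will provide month 6 data at end of study".
- y_m "is the posterior mean difference from the fitted model", so negative values favour danirixin.
- σ_trt diff "is the standard deviation (SD) of the posterior mean difference".

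The convention for z_0.9 is not defined.

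**The concern.** Two parts of the formula conflict with the text around it.

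- **The threshold.** A final posterior probability above 95% requires the final standardised difference to fall below -1.645. The threshold should lower PPS and should carry the 95% quantile. The printed term is added and carries a 90% subscript.
- **The scale.** The effect term contains m·y_m/√(mn), so it expects a per-participant-pair SD, whose square divided by m is the variance of y_m. The SAP instead supplies the posterior SD of the difference, which has already been divided by √m.

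SAP 2.3 says this interim supports decisions on further investment in danirixin and its development. An inflated PPS would make weak doses look like near-certain successes. Protocol Appendix 3 also allows interim results to be shared externally.

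**Working it through.** **Plan's own figure.** The documents report no PPS value, so there is none to reproduce.

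**Inputs.**

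- m = 75 per arm: 450/6, from SAP 3.1.3 ("When approximately 450 participants had completed 6 months of treatment") and Protocol 10.3 ("Participants will be randomized equally (1:1:1:1:1:1) to the six treatment arms").
- n = 15 per arm: Protocol 5.2 plans about 600 randomised, or 100 per arm; 90% of 100 is 90, and 90 − 75 = 15.
- Participant SD 6.5, from Protocol 10.2. The per-unit SD of a difference is σ = 6.5·√2 = 9.19, and the posterior SD is s = 9.19/√75 = 1.06. This assumes a flat prior and a simple pairwise comparison.

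**Correct form.** With y_m ~ N(θ, σ²/m), the mean of the future data has predictive distribution N(y_m, σ²(1/m + 1/n)). The final pooled mean is then distributed N(y_m, σ²·n/[m(m+n)]). Success requires that mean to be below −1.645·σ/√(m+n). Hence

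`PPS = Φ[ √(m+n)·(−m·y_m)/(σ·√(mn)) − √(m/n)·1.645 ]`

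Substituting σ = s·√m gives

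`PPS = Φ[ √((m+n)/n)·(−y_m)/s − √(m/n)·1.645 ]`

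Simulation with 1,000,000 draws gave 0.414 at y_m = −1.5 and 0.826 at −2, matching the closed form.

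**Worked values at y_m = −0.1.**

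- Correct: √6 × 0.1/1.061 − √5 × 1.645 = 0.231 − 3.678 = −3.447, so PPS = 0.0003.
- As printed: [√90 × 75 × 0.1/1.061 + √5 × 1.282]/√1125 = (67.0 + 2.9)/33.5 = 2.08, so PPS = 0.98.

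**Comparison at m = 75, n = 15.** Layout A divides both terms by √(mn), as printed. Layout B divides only the effect term, as the derivation requires.

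| y_m | Interim P(diff<0) | Correct | A, z=+1.282, SAP sigma | B, z=+1.282, SAP sigma | B, z=−1.282, SAP sigma | B, z=−1.282, sigma corrected |
|---|---|---|---|---|---|---|
| 0 | 0.50 | 0.0001 | 0.53 | 0.998 | 0.002 | 0.002 |
| −0.1 | 0.54 | 0.0003 | 0.98 | 1.00 | 0.19 | 0.004 |
| −0.333 | 0.62 | 0.0018 | 1.00 | 1.00 | 0.9999 | 0.018 |
| −0.5 | 0.68 | 0.006 | 1.00 | 1.00 | 1.00 | 0.04 |
| −1.5 | 0.92 | 0.41 | 1.00 | 1.00 | 1.00 | 0.72 |

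The value −0.333 is the smallest active-dose effect in the Protocol's planning scenarios (5 mg, Scenario 2).

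**The quantile.** Read as an ordinary quantile (+1.282), z_0.9 has both the wrong level and the wrong sign. Read as an upper-tail value (−1.282), the sign works but the rule becomes >90%. Read as the two-sided 90% value (+1.645), the level is right and the sign is wrong.

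**The sigma alone.** Layout B with z = −1.645 but the SAP's sigma still gives 0.9985 at −0.333, against 0.0018.

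**Range.** At y_m = −0.1 the printed formula gives 0.92 for m = 65, n = 25 (correct 0.0065) and 0.997 for m = 80, n = 10 (correct below 0.0001).

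**How often it would mislead.** For a dose with no true effect, y_m falls below −0.1 with probability Φ(−0.1/1.06) = 0.46. As printed, such a dose would score 0.98 or more in almost half of interims.

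**The case against.** The strongest reply has five parts.

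- **Text extraction.** The equation was machine-read from a PDF, and √(mn) under both terms cannot be right, so a subscript or sign may also have been corrupted. This is a fair caution on the quantile, and the √(mn) placement is not counted as an error here. It does not reach the definition of sigma, which is in plain prose and causes near-certainty under either layout.
- **One symbol, not two errors.** A plus sign is correct if the quantile is lower-tail (z_0.05), so level and sign could be a single subscript mistake. That is so, but the printed symbol still gives no 95% rule.
- **The formula still shows direction.** As printed, it returns about 0.03 at y_m = +0.1 and below 0.001 at +0.2. It therefore separates the right direction from the wrong one, but not a useful effect from a trivial one.
- **The program may have been right.** SAP 3.1.3 reports the interim in the past tense, and the documents contain no code and no PPS values. A write-up error is possible. However, the amendment table in SAP 1.1 describes the 7.1.1 change as clarifying the calculation used at that interim. Either the issued values or the SAP's account of them needs correcting.
- **Limited reach.** The final analysis uses the posterior probability itself, the study was not changed on this interim, and posterior means, intervals and probabilities were to be reported beside PPS. All of this stands.

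**Conclusion.** The formula is wrong as written. Its threshold term matches the >95% criterion under none of the readings tried, and its stated sigma inflates the effect term by √m, about 8.7. Under the stated assumptions, PPS is 0.98 instead of 0.0003 at −0.1, 1.00 instead of 0.006 at −0.5, and 1.00 instead of 0.41 at −1.5. Even the most generous reading, with sigma silently corrected and z_0.9 taken as −1.282, gives 0.72 instead of 0.41 at −1.5.

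These figures assume equal arms of 75, SD 6.5, a flat prior and pairwise information. The fitted dose-response model borrows across arms, so actual posterior SDs will differ; an assumed participant SD of 4.5 gives as-printed values at −0.1 of 0.977 to above 0.999 over the same range of m and n. The error is confined to the strategic-interim decision measure. Whether any issued PPS was wrong cannot be told from the documents.

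**What to change.** Replace the equation in SAP 7.1.1 with

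`PPS = Φ[ √((m+n)/n)·(−y_m)/s − √(m/n)·z_0.95 ]`

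where s is the posterior SD of the difference from placebo and z_0.95 = 1.645. Also state the rule for n = 0, which can arise because the SAP uses the actual Month 6 count when it exceeds the 90% projection. With nothing left to observe, PPS is 1 if the interim posterior probability already exceeds 95%, and 0 otherwise.

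Then recompute every PPS issued from the strategic interim using the stored posterior means and SDs, compare with the values circulated, and correct any produced with the printed formula. If the program was right, record that the SAP text was the error.

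The cost is one SAP equation and a closed-form rerun with no new model fitting. If the printed formula was used, the corrected PPS values for doses with small to moderate interim effects will be less favourable.

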##### 7.1.1.1. Endpoint

Change from baseline in Month 6 E-RS: COPD total score as defined in Section [14.6.3](#).

**7.1.1.2. Summary Measure**

For the strategic interim, the summary measure is the posterior predictive probability of success for each danirixin dose, where success is the probability that a true difference from placebo is less than 0 is >95% at Month 6.

For the final analysis, the summary measure is the posterior probability that a true difference from placebo is less than 0 at Month 6 for each danirixin dose.

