10. STATISTICAL CONSIDERATIONS

10.1. Hypothesis

The primary efficacy endpoint is the change from baseline of E-RS:COPD total score at month 6. The primary objective of the study is to study the dose response and select an appropriate dose for future drug development programs.

A model based probability inference approach in Bayesian framework will be used to guide decision-making around dose selection. The posterior probability of the change from baseline of E-RS:COPD for each active dose being less than placebo will be used.

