## 2.4. Statistical Hypotheses

The primary efficacy endpoint is the change from baseline of E-RS: COPD total score at Month 6. The primary objective of the study is to characterize the dose response of danirixin and select appropriate dose(s) for future drug development.

A model based probability inference approach in Bayesian framework will be used to guide decision-making around dose selection. The posterior probability that the change from baseline of E-RS: COPD total score for each active dose is less than placebo will be derived.

No formal statistical hypothesis will be tested in the primary efficacy analysis.

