**7.1.1.5. Statistical Analyses / Methods**

**7.1.1.5.1. Statistical Methodology Specification**

Endpoint / Variables

 
Change from baseline in Month 6 E-RS: COPD total score
 

Model Specification

Bayesian dose response model:
 
 
Models of the following form will be considered:  <math>Response = E_0 + E_{max} * f(dose)</math> 
 
Log-linear model: <math>f(dose) = \log(dose + 0.01)</math>, where 0.01 is an offset to allow the model to fit for zero dose (placebo).
 
3-parameter emax model: <math>f(dose) = dose / (dose + ED50)</math>
 
4-parameter emax model: <math>f(dose) = dose^m / (dose^m + ED50^m)</math>
 
 
 
 
Where:
 
 
<math>E_0</math> = the response at dose = 0 (placebo),
 
<math>E_{max}</math> = the maximal response over placebo,
 
<math>ED50</math> = the dose that yields 50% of the maximal response,
 
<math>m</math> = dose-response slope parameter.
 
 
 
The log-linear, 3-parameter emax and 4-parameter emax model will be fitted without adjusting for covariates. If possible, covariates (i.e., baseline, smoking status, country) will be included in the <math>E_0</math> and <math>E_{max}</math> terms of the model for the final analysis
 
Normal non-informative priors will be used for the <math>E_0</math> and <math>E_{max}</math> parameters with mean 0 and SD 100. A FUP will be used for the <math>ED50</math> and <math>m</math> parameters (Bornkamp, 2014), where the
 

prior density for the FUP is based on all the parameters in the model. An inverse -gamma prior with shape of 0.001 and scale of 0.001 will be used for the residual variance.

- Parameters will be blocked such that the MCMC procedure samples from E0 and Emax first, then the ED50 and m parameters and then finally the residual variance parameter.
- For the functional uniform priors, the density will be calculated for values of dose from 0.0001 to 50 in steps of 5 (i.e. 0.0001, 5.0001, 10.0001, ..., 50.0001).
- 3 MCMC chains will be fitted using the following starting values (as required for the parameters in each particular model):

Parameter	Chain 1	Chain 2	Chain 3
E0	Posterior mean for placebo from MMRM at Month 6 (See Section 7.1.3)	-15	15

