Emax	Posterior mean for 50mg dose from MMRM at Month 6 (See Section 7.1.3)	15	-15
ED50	25	10	50
M	1	2	4
Residual variance	6	8	10

- 100,000 MCMC samples will be generated using a thin of 50 to leave 2000 retained samples, and after a burn-in of 10,000 samples for each of the three sets of starting values. All post-burn-in samples from the 3 chains will be used for inference. The number of samples generated and the thin may be increased to reduce the ratio of the MCSE to the posterior SD, as deemed necessary.
- The seeds used to for the three chains were generated using the ranuni function in SAS and are listed in Section 14.5.2.
- The best fitting model will be the model with the smallest average DIC over the 3 chains where convergence is deemed to have been achieved. If the best fitting model is one that adjusts for covariates, all outputs will be presented adjusting for the mean in the observed covariate.
- Production and QC will be deemed to have agreement if the QC value is the following range:
  - if a number is reported to 0dp and there is a difference of  $\pm 1$  (number of participants must agree)
  - if a number is reported to 1dp and there is a difference of  $\pm 0.1$
  - if a number is reported to 2dp and there is a difference of  $\pm 0.01$
  - if a number is reported to 3dp and there is a difference of  $\pm 0.001$
  - if a number is reported to 4dp and there is a difference of  $\pm 0.0001$

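### The final primary summary measure, P(difference from placebo < 0) for each dose, is one number repeated five times and cannot help choose between doses

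*SAP*

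**What the plan says.** SAP 7.1.1.2 names one measure for the final Month 6 analysis of E-RS:COPD total score: "the summary measure is the posterior probability that a true difference from placebo is less than 0 at Month 6 for each danirixin dose". For the strategic interim, the same section says that "success is the probability that a true difference from placebo is less than 0 is >95% at Month 6". No threshold is given for the final analysis.

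The intended use is in SAP 2.4, "A model based probability inference approach in Bayesian framework will be used to guide decision-making around dose selection", followed by a statement that this posterior probability will be derived. Protocol 10.1 is similar: "The posterior probability of the change from baseline of E-RS:COPD for each active dose being less than placebo will be used". SAP 5.5 makes no multiplicity adjustment, because the modelled dose response is what will be used to pick Phase III doses.

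SAP 7.1.1.5.1 gives three candidates, each E0 + Emax × f(dose), and selects one by DIC. First, "The log-linear, 3-parameter emax and 4-parameter emax model will be fitted without adjusting for covariates". For the final analysis covariates may then be added, in the E0 and Emax terms only. On reporting: "If the best fitting model is one that adjusts for covariates, all outputs will be presented adjusting for the mean in the observed covariate".

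The results list in the same section also includes, for each dose, the posterior mean difference with a 90% credible interval, probabilities for several non-zero margins, and a fitted-curve figure overlaid with estimates from the categorical-dose MMRM.

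**The concern.** A measure offered for dose selection should be able to differ between doses. Under these models this one cannot. The report would show the same headline probability for 5 mg as for 50 mg, labelled by dose, even if the observed arm means were not monotone. A reader could take a high value at 5 mg as support from the 5 mg data, when it may come almost entirely from the higher doses. If the interim success criterion of more than 95% were applied to the final fit, all five doses would meet it or none would.

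**Working it through.** **1. The plan's own figure.** Protocol 10.2 says that with 600 participants the 90% interval for 35 mg versus placebo excludes 0 in over 80% of simulations under all scenarios. Inputs: SD 6.5, the 35 mg effects in Table 4 (-2.5, -1.667, -2), and 600/6 = 100 per arm.

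- Pairwise: SE = 6.5 × √(2/100) = 0.919. Power = Φ(|effect|/0.919 - 1.645) = 0.859, 0.567 and 0.702 for scenarios 1, 2 and 3. This misses 80% in two scenarios.
- Model-based: the 3-parameter Emax gives 0.984, 0.829 and 0.885, and the 4-parameter Emax 0.998, 0.863 and 0.900. (Simulated, SD fixed at 6.5, assumed ranges ED50 0.05 to 75 and m 0.5 to 6; the rate is how often P(Emax < 0) exceeds 0.95.)

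The stated figure is reproduced by the model, which pools across doses. By step 2, each of these model-based rates is the same at 5 mg as at 35 mg.

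**2. The identity.** The difference from placebo at dose d is Emax × [f(d) - f(0)].

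| Model | f(d) - f(0) | From 5 mg to 50 mg |
|---|---|---|
| Log-linear | log((d + 0.01)/0.01) | 6.22 to 8.52 |
| 3-parameter, ED50 = 25 | d/(d + ED50) | 0.17 to 0.67 |
| 4-parameter, ED50 = 25, m = 4 | d^m/(d^m + ED50^m) | 0.0016 to 0.94 |

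The bracket is positive at every active dose whenever ED50 > 0 and m > 0. In each draw the difference therefore has the sign of Emax (the slope, in the log-linear model) at all five doses, and the five probabilities equal P(Emax < 0). With covariates in E0 and Emax and outputs at the covariate mean, the common value is P(Emax at the covariate mean < 0). For the same reason an equal-tailed model-based 90% credible interval excludes 0 at all doses or at none.

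**3. One illustrative dataset.** Assumed arm means are 0, +0.5, -1, -2, -2, -1 (placebo, then 5 to 50 mg), with SD 6.5 and 540/6 = 90 per arm. The direct comparison has SE = 6.5 × √(2/90) = 0.969; at 5 mg, Φ(-0.5/0.969) = 0.30.

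| P(difference < 0) | 5 mg | 10 mg | 25 mg | 35 mg | 50 mg |
|---|---|---|---|---|---|
| Direct, arm versus placebo | 0.30 | 0.85 | 0.98 | 0.98 | 0.85 |
| Log-linear | 0.978 | 0.978 | 0.978 | 0.978 | 0.978 |
| 3-parameter Emax | 0.991 | 0.991 | 0.991 | 0.991 | 0.991 |
| 4-parameter Emax | 0.991 | 0.991 | 0.991 | 0.991 | 0.991 |

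With an assumed 70 per arm, to allow for per-protocol exclusions and the 10-day diary rule, the model values are 0.962, 0.981 and 0.979, again equal across doses. P(difference < -1.5) does separate 5 mg from 50 mg at 90 per arm: 0.31 and 0.57 (log-linear), 0.02 and 0.69 (3-parameter), 0.02 and 0.68 (4-parameter).

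The decimals depend on the functional uniform prior. The SAP says only that the "prior density for the FUP is based on all the parameters in the model", so three readings were tried: the gradient in ED50 and m only; that times |Emax| (3-parameter) or Emax² (4-parameter); and the gradient in all parameters. Across them the named measure is 0.98 to above 0.99 at 90 per arm and 0.96 to above 0.99 at 70.

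A separate MCMC fit of the 4-parameter model to these arm means, with unknown variance, smoking status in E0 and Emax and 6,000 retained draws, gave 0.9897 at every dose and P(Emax < 0) = 0.9897. The equal-tailed 90% intervals were -1.463 to -0.003 at 5 mg and -3.20 to -0.58 at 50 mg.

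**4. Over repeated trials.** Under Scenario 2 of Table 4 (2,000 trials per cell, each model fitted alone, SD known), the named measure exceeds 0.95 in 67 to 95% of trials at 90 per arm and 57 to 90% at 70, as often at 5 mg as at 50 mg. The direct comparison at 90 per arm does so in Φ(-1.645 + 0.333/0.969) = 9.7% at 5 mg and Φ(-1.645 + 2/0.969) = 66.2% at 50 mg.

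**The case against.** The strongest reply is that the dose-level information is already planned. SAP 7.1.1.5.1 reports estimates, intervals and several margins per dose, and the Bayesian MMRM in SAP 7.1.3.5.1 gives the same probabilities with dose as a category. The equality would be visible in the table. SAP 2.4 disclaims formal testing, no final threshold exists, and pooling on direction is the purpose of a monotone model: within the model, P(difference < 0) at 5 mg is a valid statement. The dataset in step 3 is invented, all Table 4 scenarios are monotone, and Protocol 10.5.1.1 keeps a quadratic alternative under which the identity can fail.

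Most of this is true and limits the point. It concerns the named measure only, not the whole plan, the interim predictive probability, the completed futility analysis or a quadratic fit. The simulated ranges are illustrations and carry no weight for the identity. What the reply does not answer is that the one measure named in SAP 7.1.1.2, and singled out in SAP 2.4 and Protocol 10.1, cannot vary by dose under any SAP candidate, and the SAP nowhere says so. One further point stands: demoting a probability that the protocol says will be used is a departure that should be recorded.

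**Conclusion.** The point holds and should be fixed. Within any fit of the three SAP models, the measure is exactly one number at all five doses. It is evidence that danirixin has an effect in the favourable direction, not separate evidence for an individual dose. This rests on ED50 > 0 and m > 0. The SAP prints no bounds, but it defines ED50 as a dose and all starting values are positive. It does not depend on the data, the prior or the sample size. The gap from a direct comparison (0.30 against about 0.98 or more at 5 mg in the example) does depend on assumed means, SD 6.5, the prior reading and the number analysed.

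**What to change.** Amend SAP 7.1.1.2 and 2.4 as follows.

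1. Report P(Emax < 0) once, as global evidence of a dose response.
2. Name as dose-specific measures the posterior mean difference with 90% credible interval and all the non-zero-margin probabilities already listed in SAP 7.1.1.5.1 (below -0.5, -1, -1.5 and -2). Do not single out one margin now: the dose-response table was a deliverable of the unblinded strategic interim (SAP 3.1.3 and 14.11.5). If one is chosen, state that the choice followed that interim.
3. State that P(difference < 0), and whether an equal-tailed model-based 90% interval excludes 0, are the same at every dose. Specify the interval type in SAP 7.1.1.5.1, as 7.1.3.5.1 does for the MMRM.
4. Cite the overlaid MMRM estimates as supportive dose-level evidence. Note their different handling of intercurrent events: hypothetical with missing at random in SAP 7.1.3.4, Month 6 data only in 7.1.1.4.
5. List the departure from Protocol 10.1 in SAP Table 1.

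The cost is wording; no model, dataset or display changes. The headline is no longer a single probability per dose.
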